**Secondary outcome:**

- **Postoperative pain:** will be recorded on a Numerical Rating scale (NRS), pain intensity will be recorded preoperatively and postoperatively after 6, 12, 24, 48, 72 hours and 7 days. The NRS consists of a 10-cm line anchored by two extremes "No pain" and "pain as bad as could be", patient will be asked to choose the mark that represent their level of pain. Pain level will be assigned to one of 4 categorical scores: **1**, None(0); **2**, Mild(1-3); **3**, Moderate(4-6); **4**, Severe (7-10).

Outcome	Tool	Unit	Time
Postoperative pain	Numerical rating scale NRS 	Categorial data	Immediately after treatment and Up to 7 days after endodontic treatment

### 13. Participants time line

STUDY PERIOD									
Time point	T0	T1	F1	F2	F3	F4	F5	F6	F7
Activity									
Enrollment									
Eligibility criteria	x								
Informed consent		x							
Allocation		x							
Intervention									
Access		x							
Initial sample		x							
Cleaning and shaping		x							
Final sample		x							
Obturation		x							
Assessment									
Intracanal bacterial count		x							
Postoperative pain			x	x	x	x	x	x	x

T0: Enrollment of the patient after diagnosis and radiographic evaluation.

T1: Signing the informed consent and allocation of the patient to either intervention or control group. Starting the procedure, taking the first root canal sample before cleaning and shaping, second root canal sample after cleaning and shaping, obturation.

F1: Patients will be asked to evaluate their postoperative pain levels using a numerical rating scale (NRS)

F2: similarly, at 6 hours.

F3: similarly, at 12 hours.

F4: similarly, at 24hours.

F5: similarly, at 48 hours.

F6: similarly, at 72 hours.

F7: similarly, at 7 days.

### 14. Sample Size:

- The aim of the current study is to compare the antimicrobial effects of Nano chitosan, Chlorhexidine, Chlorhexidine/ Nano Chitosan combination to NaOCl in patients with necrotic mandibular posterior teeth. Based on a previous study by Shingare & Chaugule 2011 the difference in bacterial count between at least 2 groups is 75±75.

Using power 80% and 5% significance level we will need to study 17 in each group. This number is to be increased to a sample size of 20 to compensate for losses during follow up. Sample size calculation was achieved using PS: Power and Sample Size Calculation Software Version 3.1.2 (Vanderbilt University, Nashville, Tennessee, USA).

## **15. Recruitment strategy:**

- [name]. will select patients from the outpatient clinic of the Department of Endodontics, Faculty of Dentistry, Cairo University, Egypt.
- "Screening of patients will be carried on until the target population is achieved".
- "Identifying and recruiting potential subjects is achieved through patient database".

## **16. Allocation**

### **16.a. Randomization:**

**Sequence generation:** using computer-generated random numbers.

- List will be created on (<https://www.random.org/>), the patients will be randomly classified into four groups:
  - "Group A: Irrigation with Nano chitosan".
  - "Group B: Irrigation with Chlorhexidine
  - "Group C: Irrigation with Chlorhexidine/Nano Chitosan combination".
  - "Group D: Irrigation with 5.25% Sodium Hypochlorite".
- Allocation ratio will be 1:1.
- This method will be done by the co-supervisor.

### **16.b. Allocation – concealment mechanism:**

- According to the allocation sequence obtained from the computer software, the numbers that generate randomly from the software will be written in small folded opaque papers then insert into Envelope. (Opaque sealed envelope and sign across sea).
- All those papers will be ready before conducting any procedure. This method will be done by the co-supervisor. That Envelops will be placed in a container (box), each participant will grasp one envelope blindly before operation and will be assigned accordingly. The number of papers will decrease as each patient picks his number and so on.

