##### **- Preoperative measures (for all groups):**

- Medical and dental history will be obtained from all patients participating in this research. Clinical and radiographic evaluation for each tooth included in this study will be recorded.
- Pain scale chart will be given to each patient to rate his /her pain level before endodontic treatment as preoperative reading on an NRS scale.
- Tooth will be anaesthetized using 1.8 ml Mepivacaine HCl 2% - Levonordefrin 1:20000 (Carpule Mepecaine-L, Alexandria Company for Pharmaceuticals and Chemical Industries, Egypt).
- The tooth will be isolated with rubber dam to maintain aseptic field, after isolation the tooth and surrounding field will be disinfected by a protocol using 3% hydrogen peroxide 2.5% sodium Hypochlorite before and after coronal access cavity preparation.
- The initial sample S1 will be collected from root canals before preparation using sterile # 15 paper points.

- Sterile saline solution will be injected in the canals followed by the insertion of a #15 K-file (Mani, Japan) to at least 1 mm short of the apex as confirmed by apex locator (Root ZX, J.Morita USA, Irvine, CA) to facilitate the insertion of the paper points to collect the samples.
- Each paper point will remain in place for at least 1 minute then immediately placed in test tubes containing reduced transport fluid and sent to the Microbiology Laboratory, Faculty of Medicine, Cairo University for microbiologic processing.
- Root canals will be mechanically prepared in a crown-down approach using the rotary files (M-Pro file system) in an endodontic motor (X-Smart, Dentsply Maillefer, USA) according to the manufacture instructions.

The following sequence will be used for all groups:

- # 18 file taper (orifice opener) 0.09 will be used to prepare two thirds of estimated working length.
- # 20 file taper 0.04 will used to full working length.
- #25 file taper 0.06 will used to full working length.
- #35file taper 0.04 will used to full working length.
- The canals will be thoroughly irrigated for 1 minute between every two subsequent files using 2 ml of 2.5% NaOCl.
- After complete preparation all canals will be flushed with EDTA followed by sterile saline.
- **Intervention for test group A**
  - After complete preparation, the canals will be flushed using 5 ml of Nano chitosan (Nano tech, Egypt) in a plastic syringe using Navitip needles (Ultradent, South Jordan,UT).

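### The arm is assigned before the operation and no stated rule withholds it from the operator, although all arms are treated identically until the final flush

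*Combined protocol and SAP*

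**What the plan says.** **Time of assignment.** Section 16.b says that "each participant will grasp one envelope blindly before operation and will be assigned accordingly". In section 13, the description of visit T1 runs in the same order: "allocation of the patient to either intervention or control group. Starting the procedure, taking the first root canal sample before cleaning and shaping".

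**Who assigns.** Under section 16.b, "the numbers that generate randomly from the software will be written in small folded opaque papers", which the co-supervisor prepares and places in sealed envelopes. Section 16.c has the investigator pass participants' numbers to the co-supervisor, who generates the sequence and assigns the group. Neither section says who opens the envelope, or when the operator is told the arm.

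**Who is masked.** Sections 8, 16.c and 17 name participants and assessors (in sections 8 and 17, the laboratory assessors). The operator is not named. Section 8 also says that one person carries out the trial.

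**Where the arms diverge.** Section 11.a describes isolation, disinfection, access and S1 under measures for all groups. It introduces the rotary files with "The following sequence will be used for all groups". Irrigation during preparation is also common: "The canals will be thoroughly irrigated for 1 minute between every two subsequent files using 2 ml of 2.5% NaOCl". So is the last step before the tested solutions: "After complete preparation all canals will be flushed with EDTA followed by sterile saline". The groups first differ at the 5 ml flush that follows.

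**What is measured.** Section 12 defines the primary outcome through colony-forming units counted at S1 and S2.

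**The concern.** An operator who knows the arm may sample or prepare a canal differently without intending to, for example by being more thorough when an unproven solution is to follow. A single operator makes this matter more, because any arm-related habit would not be averaged over several people. Masking the laboratory protects the counting of colonies. It cannot undo a difference in how a sample was taken or a canal was cleaned.

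The exposure is avoidable for a large part of the procedure. Nothing before the final flush depends on the arm, so the operator could do all of it without that knowledge. If the plan does not secure this before enrolment, the analysis cannot restore it afterwards.

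**Working it through.** The plan gives no figure on this point, so the check sets the sections side by side.

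| Stage, in order | Where | Depends on arm? | Fixed by the plan | Left open |
|---|---|---|---|---|
| Envelope draw, assignment | 13 (T1), 16.b | – | Before the operation | Who opens the envelope; when the operator learns the arm |
| Isolation, disinfection, access | 11.a | No | Disinfecting agents | – |
| Saline, K-file, S1 | 11.a | No | File and paper-point size | Saline volume; number of paper points; exact dwell time and file position |
| Rotary preparation with irrigation | 11.a | No | File sequence; irrigant concentration, volume and time | – |
| EDTA, then saline | 11.a | No | Order | Volumes |
| Final flush | 11.a | **Yes** | 5 ml | – |
| Saline rinse | 11.a | No, but the arm is already in use | 10 ml | – |
| S2 | 11.a | No, but the arm is already in use | Same manner as S1 | As for S1 |

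Four things follow.

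1. **The arm is not needed before the final flush.** Every earlier stage is common to the four groups, yet assignment precedes all of them.
2. **Early operator knowledge is possible but not shown.** The papers carry numbers and the co-supervisor assigns, so the operator might hold only a code. The plan does not say so. The content of the roles and responsibilities item in the administrative information is not in the text available for review and might bear on this.
3. **Some discretion remains before the flush.** The paper-point time is a minimum, "Each paper point will remain in place for at least 1 minute", and the file position is a limit, "to at least 1 mm short of the apex as confirmed by apex locator". The volumes of the saline before S1, the EDTA and the saline after it are not stated. The other main elements of preparation are fixed, which narrows the scope for bias.
4. **The route into the result is only partly defined.** Section 12 counts colonies at both samples. Neither section 12 nor section 20 says whether the groups are compared on S2 alone, on the change from S1, or with adjustment for S1. An arm-related difference in taking S1 would reach the comparison only if S1 enters it. A difference in preparation could reach S2 under any of these choices.

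The fix leaves the sample size alone. Section 14's 17 per group reproduces: a difference of 75 with SD 75, two-sided 5% and 80% power gives 16.71 by the two-sample t-test, rounded up to 17. The rise to 20 implies an allowance of 1 − 17/20 = 15%. Four groups of 20 give 4 × 20 = 80 cases.

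**The case against.** The strongest reply is that the plan never promised a masked operator. Section 8 defines double blinding as covering the participant and the laboratory assessor, and sections 16.c and 17 are consistent with that. Allocation after consent and before the procedure is not in itself a defect. The point also rests on silence, and part of that silence may be filled by the roles section. All of this stands. It is why the point is an avoidable weakness and a request to write down a rule, not a charge of inconsistency.

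A second reply is that the remaining discretion is a gap in standardisation whether or not the operator is masked, and that the most exposed steps (the flush and S2) stay unmasked under any version of the fix. This also stands. The gain is partial and its size is unknown. It still closes one route to bias at little cost.

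A third reply is practical. Section 11.a provides only local anaesthesia, so a patient who is awake could overhear the arm if it is announced at the chair, and that patient later reports pain on the numerical scale in section 12. This is right, and the fix has to deal with it.

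Three stronger readings are tempting, and the documents do not support them:
- That the operator does know the arm from the start. The plan leaves this open.
- That a bias in S1 passes straight into the primary result. The plan does not say how S1 is used.
- That the share of steps, or of irrigant volume, delivered before the flush measures the problem. Such counts depend on how steps are grouped or on adding unlike solutions, and neither measures operator bias.

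**Conclusion.** The concern holds in a limited form. The plan assigns the arm before the operation, treats all arms identically until the final flush, and states no rule that keeps the arm from the operator in between. It therefore permits, without establishing, that one unmasked operator takes S1 and carries out the shared preparation. A difference introduced there could reach the colony counts despite laboratory blinding.

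The size of any bias cannot be estimated from the documents. The standardised file sequence and irrigation limit it. The conclusion assumes that the roles section sets no disclosure rule; if it does, what remains is to repeat that rule where allocation and blinding are described. Because operator masking is not claimed, nothing here contradicts the plan. The change should be made as a cheap improvement before enrolment.

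**What to change.** Keep the co-supervisor's opaque sealed envelopes and the draw before the operation, and change the text as follows.

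- **Sections 13 (T1), 16.b and 16.c:** state that the envelope stays sealed until S1, full preparation, EDTA and saline are complete, and is opened immediately before the final flush. Name by role who opens it.
- **Same sections:** require that the arm is disclosed silently or by code, so that the patient does not learn it.
- **Sections 16.b and 16.c:** reconcile the two accounts of assignment, one in which the participant draws an envelope and one in which the co-supervisor assigns.
- **Section 17:** state that the operator is masked up to the final flush only, and record as a limitation that the flush and S2 are unmasked.
- If the roles section already holds such a rule, repeat it in sections 16 and 17.

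The cost is a text change, with no added patients, visits, samples or staff. The downsides are that all four solutions must be available for each of up to 80 cases, and that there is a short pause before the flush while the arm is disclosed.

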### **16. c. Allocation - Implementation:**

- Principle investigator ([name]) will referee all participants' number to the co-supervisor who will generate the random sequence, and assign the patients for intervention or control group. Neither the assessor nor the patients know the criteria of allocation.

## **17. Blinding:**

- "Blinded participants: The patient will be informed of the steps of the treatment (as mentioned in the consent form) without getting into details".

- "Blinded Assessors: Blinding to the laboratory assessors is done by not involving them in sequence generation or allocation concealment or treatment options".

### **C) Data collection, management, and analysis:**

#### **18. Data collection methods:**

- Base line data will be recorded on a personal history chart prior to clinical examination.
- Antimicrobial efficacy will be measured by counting the number of colony forming units CFU of bacteria after cultivating the collected samples.
- Paper based pain scale (VAS) assessments will be filled by the patient preoperatively, and postoperatively after 6, 12, 24, 48,72 hours and after7 days.

#### **19. Data management:**

- Patient files will be stored in numerical order and stored in secure and accessible place. [name] will assignee each patient a folder containing all their data including primary and secondary outcomes, patient's data recorded as a hard copy with the signed consent. "Also, a soft copy of the data will be kept on operators' laptops and will be backed up on an external hard disk".
- All data will be maintained in storage for 1 year following completion of the study.

#### **20. Statistical methods:**

- Data will be analyzed using IBM SPSS advanced statistics (Statistical Package for Social Sciences), version 21 (SPSS Inc., Chicago, IL). Numerical data will be described as mean and standard deviation or median and range. Data will be explored for normality using Kolmogrov-Smirnov test and Shapiro-Wilk test. Comparisons between 4 groups for normally distributed numeric variables will be done using the ANOVA while for nonnormally distributed numeric variables will be done by Kruskal Wallis test. A p-value less than or equal to 0.05 will be considered statistically significant. All tests will be two tailed.
- Categorical data will be described as numbers and percentages and comparisons will be done by chi square test or fisher exact as appropriate

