**12. Outcomes:**

**Primary outcome:**

- **Antibacterial efficacy:** will be assessed by counting the number of colony forming units (CFU) before and after irrigation (S1 and S2) for each patient. Collected samples will be cultured in serial dilution on blood agar plates, incubated for 24 hours, and then the number of colony forming units (CFUs) will be counted per ml.

Outcome	Tool	Unit	Time
antibacterial efficacy	Number of CFUs 	Numerical data	Samples collected before and after preparation and transferred to the laboratory for immediate cultivation.

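### The primary analysis variable, its scale and the use of S1 are left open, and neither test selected by the normality screen adjusts for the S1 count taken in every patient

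*Combined protocol and SAP*

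**What the plan says.** Section 20 (Statistical methods) is the whole analysis plan. It states "Data will be explored for normality using Kolmogrov-Smirnov test and Shapiro-Wilk test". Comparison of the four groups "for normally distributed numeric variables will be done using the ANOVA while for nonnormally distributed numeric variables will be done by Kruskal Wallis test". The other operative statements are "A p-value less than or equal to 0.05 will be considered statistically significant" and "All tests will be two tailed".

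The section does not give a threshold for the normality tests, a rule for when they disagree, or the unit they apply to (each arm, the pooled data or residuals). It names no transformation and no covariate, and it does not say which numeric variable is the primary one.

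Section 12 (Outcomes) defines antibacterial efficacy by CFU counts "before and after irrigation (S1 and S2) for each patient", so a baseline exists for everyone. It does not say whether S2 alone, the change, or a percent or log reduction is compared between arms.

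Section 14 (Sample Size) plans on an untransformed scale: "the difference in bacterial count between at least 2 groups is 75±75". It concludes "Using power 80% and 5% significance level we will need to study 17 in each group", raised to 20 for losses.

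**The concern.** There are two separate problems.

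**The choice of test.** It is made after the data are seen, by two procedures that can point in different directions. ANOVA compares means and Kruskal-Wallis compares rank distributions, so the hypothesis tested also depends on the data.

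**The unspecified variable and the unused baseline.** Initial bacterial load is likely to vary between patients, and S1 measures it at no extra cost, but neither named test adjusts for it. Because the primary variable is not named, several analyses would all comply with section 20, and they can give different answers. At stake are the credibility of the single primary result and power that could be had without recruiting anyone.

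**Working it through.** **1. The plan's own figure.** Inputs from section 14: difference 75, SD 75, two-sided 5%, power 80%. Standardised difference = 75/75 = 1.0. The exact two-sample t test has power 0.781 at 16 per group and 0.807 at 17, so 17 reproduces. 17/0.85 = 20 implies an allowance of 15% for losses. This calculation is for one two-group comparison without a baseline, whereas section 20 specifies a four-group test.

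**2. Does the screen do damage?** (Lognormal data; Shapiro-Wilk, or Kolmogorov-Smirnov with the Lilliefors correction, in each arm at 0.05; ANOVA only if all four arms pass.)
- Type I error of the two-stage rule: 0.042-0.056. Always taking the smaller of the ANOVA and Kruskal-Wallis p-values: 0.053-0.070.
- The two normality tests select different analyses in 16-20% of trials when data are normal or mildly skewed, and in under 1% when the natural-log SD is 1 or more.
- The final verdict changes far less often. It changed in 0.3% of trials at CV 1 with one arm twofold higher (20 per arm). At CV 0.5 it changed in 0.7% with no effect and 2.7% with a ratio of 1.4.

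**3. What does S1 buy?** Adjusting for a baseline with correlation ρ multiplies residual variance by 1 − ρ². For ρ = 0.3, 0.5, 0.7 this is 0.91, 0.75, 0.51.

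Analytical check for the four-group F test at n = 17, with arm means 0, 0.5, 0.5, 1 SD. The mean is 0.5 and the sum of squared deviations is 0.25 + 0 + 0 + 0.25 = 0.5. The noncentrality is λ = 17 × 0.5/(1 − ρ²).

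| ρ | λ | Power |
|---|---|---|
| S1 not used | 8.50 | 0.654 |
| 0.3 | 8.50/0.91 = 9.34 | 0.699 |
| 0.5 | 8.50/0.75 = 11.33 | 0.790 |
| 0.7 | 8.50/0.51 = 16.67 | 0.929 |

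Simulation of the section 20 rule applied to S2, against ANCOVA of log10(S2+1) on arm and log10(S1+1). Assumptions, none of them in the documents: lognormal-Poisson counts, CV 1, S2 geometric mean 100 CFU, one arm twofold higher, very few zeros, 17 per arm.

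| Assumed ρ | Section 20 rule on S2 | Log-scale ANCOVA |
|---|---|---|
| 0 | 0.62-0.65 | 0.66 |
| 0.3 | 0.62-0.65 | 0.72 |
| 0.5 | 0.62-0.65 | 0.79 |
| 0.7 | 0.62-0.65 | 0.91 |

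The rule does not use S1, so its power does not depend on ρ; the range covers the runs. Type I error is near 5% for both methods. The ρ = 0 row isolates test and scale, which are worth at most about 4 points. The rest of the gain comes from S1.

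**4. What does the open variable cost?** Under no effect, with S1 geometric mean assumed at 10,000, reporting the smallest p-value among screened S2, raw change and percent reduction gives a false-positive rate of 11-14%. A change score is also no substitute for adjustment. With the arm means of the analytical check, Kruskal-Wallis on log change has power 0.46-0.48 at ρ = 0.3 and 0.61-0.63 at ρ = 0.5, against 0.61-0.63 for Kruskal-Wallis on S2 alone.

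**5. Zeros.** The Review of literature cites a clinical study in which 44% and 40% of canals were still contaminated after preparation, so 56% and 60% were negative (midpoint 58%). If 58% of S2 counts are set to zero at random, power is about 0.06-0.07 for both methods and the advantage of ANCOVA is gone.

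**The case against.** Several stronger readings are tempting and should not be drawn.

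- **That the plan has decided to analyse raw CFU and ignore S1.** Section 20 is silent, and section 12 defines efficacy by both samples, so a change or percent reduction is compatible with the text. The supportable statement is that variable, scale and use of S1 are unspecified. Neither ANOVA nor Kruskal-Wallis adjusts for S1 under any of these readings.
- **That the screen inflates type I error, or that the verdict turns on which normality test is followed.** Step 2 shows neither to a material degree. ANOVA and Kruskal-Wallis do reach opposite 5% verdicts in about 19% of trials in the CV 1 setting, but that compares two tests run freely. Under that skew both normality tests almost always lead to Kruskal-Wallis. Much higher disagreement (64-87%) arises only for a Kolmogorov-Smirnov test without correction for estimated parameters, which the plan does not specify.
- **That an SD equal to the planning difference demonstrates skew.** It does not. Section 14 gives no arm means, and a between-group difference carries no information on shape.
- **That a fixed power loss follows.** The size rests on an assumed correlation.

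The fair defence is therefore that the rule is conventional and roughly valid, that scale is irrelevant on the Kruskal-Wallis branch when S2 is analysed, and that a log analysis has its own difficulty with zeros. All of this stands. It does not supply the missing primary variable or recover the information in S1. In none of the settings examined did ANCOVA do materially worse than the section 20 rule; with many zeros the two were level.

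**Conclusion.** The point holds in a limited form. Section 20 leaves the primary variable, its scale and the role of S1 open, and selects between two unadjusted tests by a screen with no rule for disagreement. The screen is a minor weakness. The unnamed variable and the absence of baseline adjustment are the substantive ones.

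If S2 is analysed, the forgone power at 17 per arm runs from almost nothing at ρ = 0 to more than 25 points at ρ = 0.7 (0.91 against 0.62-0.65). At ρ = 0.5 it is 14 to 17 points (0.79 against 0.62-0.65). These figures assume CV 1, a twofold difference in one arm, an S2 geometric mean of 100 CFU and few zeros. With most S2 counts at zero, neither approach has useful power in the setting examined. The change is worth making before analysis; the current rule does not make the trial's test invalid.

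**What to change.** Rewrite the primary-outcome part of section 20.

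1. Drop the normality screen for the primary outcome.
2. Name S2 (CFU/ml) as the analysis variable.
3. Prespecify one analysis: ANCOVA of log10(S2+1) on arm with log10(S1+1) as covariate. Report the three contrasts against NaOCl as geometric mean ratios with 95% confidence intervals.
4. Prespecify a rule for zeros. For example, if more than a stated share of S2 counts is zero, use rank ANCOVA of S2 adjusted for S1 and report the proportion of negative cultures by arm. Fix the share in advance and judge it on counts pooled over arms, so that it does not become another discretionary switch.
5. Keep Kruskal-Wallis on S2 as a named sensitivity analysis, reported whatever the data look like.

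The cost is about one paragraph, with no new data or patients. The downsides are that results are read as ratios instead of CFU differences, and that those ratios depend on the +1 offset when zeros are common.

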## **7. Objectives:**

### **- Research hypothesis:**

There is no difference in the antimicrobial efficacy among Nano chitosan, Chlorhexidine, Chlorhexidine/Nano Chitosan and Sodium hypochlorite in root canal treatment.

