### **- Primary objective:**

The primary objective of this study is to assess the antimicrobial efficacy of Nano-chitosan, chlorhexidine and Chlorhexidine/Nano Chitosan combination versus NaOCl.

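### Section 20 plans only a four-group omnibus test of CFU, so the primary objective's three comparisons with NaOCl have no planned test or confidence interval, and the use of S1 and S2 is left open

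*Combined protocol and SAP*

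**What the plan says.** All references are to the combined protocol and SAP.

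- **Objective (section 7).** The primary objective is to "assess the antimicrobial efficacy of Nano-chitosan, chlorhexidine and Chlorhexidine/Nano Chitosan combination versus NaOCl". The aim at the end of the rationale in section 6 has the same structure: three irrigants, each set against NaOCl.
- **Hypothesis (section 7).** The research hypothesis is global: "There is no difference in the antimicrobial efficacy among Nano chitosan, Chlorhexidine, Chlorhexidine/Nano Chitosan and Sodium hypochlorite".
- **Outcome (section 12).** Antibacterial efficacy is assessed by "counting the number of colony forming units (CFU) before and after irrigation (S1 and S2", per patient, in CFU per ml.
- **Analysis (section 20).** For numeric variables: "Comparisons between 4 groups for normally distributed numeric variables will be done using the ANOVA", with Kruskal-Wallis if the data fail a normality check. Tests are two-tailed and "A p-value less than or equal to 0.05 will be considered statistically significant". Numeric data are also summarised by mean and SD or by median and range.
- **Sample size (section 14).** The basis is that "the difference in bacterial count between at least 2 groups is 75±75". Then: "Using power 80% and 5% significance level we will need to study 17 in each group", and "This number is to be increased to a sample size of 20 to compensate for losses during follow up". No test and no pattern of the four means is named.

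No section names a contrast with NaOCl, a post hoc procedure, a multiplicity rule or a confidence interval.

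**The concern.** A significant four-group test says that the groups are not all alike. It does not say whether any given irrigant differs from NaOCl; the signal could lie between two of the test irrigants. A non-significant result gives no interval showing how large a difference from NaOCl remains plausible. Either way, the comparison that the primary objective asks for gets no planned inference.

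The analysed variable is also open. S2 alone, raw change, percent reduction and log reduction can lead to different conclusions from the same counts, and the plan does not choose among them. The choice between ANOVA and Kruskal-Wallis depends on the data as well. Variable and test could therefore both be settled after the counts are known. The same holds for any NaOCl comparisons added at that stage, and for whether they are adjusted.

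**Working it through.** **1. The plan's own figure.** Inputs from section 14: difference 75, two-sided alpha 0.05, power 80%. Assumption: the second 75 is the common SD, so the standardized difference is d = 75/75 = 1. For a two-sample t-test with n per group, df = 2n − 2 and the noncentrality is d·√(n/2).

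- n = 16: power 78.1%
- n = 17: √(17/2) = 2.92, power 80.7%
- n = 20: √(20/2) = 3.16, power 86.9%

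The smallest n reaching 80% is 17, the stated figure. Allowing 15% loss, 17/0.85 = 20.

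**2. Power of the test that section 20 does plan.** One-way ANOVA, four groups, df = 3 and 4(n − 1), noncentrality λ = n·Σ(mᵢ − m̄)². The means mᵢ are in SD units and span 1 SD.

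| Pattern of means | Σ(mᵢ − m̄)² | λ at n=17 | Power n=17 | Power n=20 | n for 80% |
|---|---|---|---|---|---|
| 0, ½, ½, 1 | 0.50 | 8.50 | 65% | 74% | 23 |
| 0, ⅓, ⅔, 1 | 0.556 | 9.44 | 71% | 79% | 21 |
| 0, 0, 0, 1 | 0.75 | 12.75 | 84% | 90% | 16 |
| 0, 0, 1, 1 | 1.00 | 17.00 | 93% | 97% | 12 |

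So 80% at 17 per group holds for some patterns and not for others. Section 13 places both samples at visit T1. Loss to follow-up should therefore matter little for CFU, and n = 20 is the more relevant size unless samples fail.

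**3. Error rate if NaOCl contrasts are added later.** This is conditional, because the plan contains no such tests. Three contrasts share the NaOCl arm and use a pooled variance, each tested at 0.05 (simulation with normal data and equal variances, n = 17 and n = 20):

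- no ANOVA gate, all groups equal: about 12%
- run only after a significant ANOVA, all groups equal: about 4%
- run only after a significant ANOVA, one test arm 1 SD away (error on the two remaining null contrasts): about 9%

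**4. Power of prespecified contrasts.** Two-sided Dunnett with three contrasts has critical value 2.406 at df 64 (n = 17) and 2.397 at df 76 (n = 20), a per-contrast p of about 0.019. With noncentrality d·√(n/2) and no use of S1:

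- d = 1: 69.4% at n = 17, 77.6% at n = 20
- d = 0.8 and d = 1.2 at n = 20: 55.5% and 91.6%
- 80% power at n = 20 needs d = 1.03
- half-width of the simultaneous 95% interval at n = 20: 2.397·√(2/20) = 0.76 SD

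With S1 as covariate and an assumed S1–S2 correlation of 0.3, power is 73–74% at n = 17 and 81–82% at n = 20. At zero correlation the covariate costs about 1 percentage point. The documents give no correlation.

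**The case against.** The omnibus test is not misplaced: it answers the only hypothesis that the protocol states, and it fits the formulated question in section 6, which asks whether effects differ. That stands. The gap is against the primary objective and the aim.

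A reader might infer that the trial could say nothing about a single irrigant against NaOCl. The documents do not support that. Section 20 plans group means or medians, so the direction and size of observed differences will be visible. What is missing is a test and an interval for them.

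A reader might also infer that the plan inflates its error rate. It does not, since it contains no pairwise tests. Even if contrasts were added behind a significant ANOVA, error under the global null would stay at about 4%. The inflation to about 9% or 12% arises only in the other two situations above.

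Nor does the match at 17 prove that the sponsor intended a pairwise t-test; section 14 names no test. And S1 is part of the outcome definition in section 12. What is open is how it enters the comparison.

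Post hoc testing is customary and might be taken as understood. That is a reason to write it down, because the method and any adjustment would otherwise be chosen with the data in view.

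**Conclusion.** The point holds in this form, and it should be fixed before analysis because it concerns the primary outcome. As written, section 20 gives no inference for any irrigant against NaOCl and leaves open how S1 and S2 form the analysed variable. The sample size reproduces for a test that section 20 does not contain, while the planned ANOVA has between 65% and 93% power at 17 per group (74% to 97% at 20).

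The absence of contrasts, intervals and a defined CFU variable rests on the text alone. The power figures rest on normal data, equal variances and a standardized difference of 1, reading the second 75 in section 14 as an SD. The documents do not show that this effect on raw counts carries over to a log scale.

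**What to change.** 1. In section 20, name one primary variable: log10 S2 CFU/ml, with a fixed rule for zero counts, analysed by ANCOVA on group with log10 S1 as covariate. For the primary outcome this replaces the normality-test choice between ANOVA and Kruskal-Wallis. Do not switch to a rank method after seeing the data; list any rank-based analysis as a prespecified sensitivity analysis.
2. Make the three contrasts with NaOCl primary, with Dunnett adjustment and simultaneous 95% confidence intervals. Make all other pairs secondary.
3. In section 14, restate the power for these contrasts: about 69% at 17 and 78% at 20 per group without S1 at an assumed standardized difference of 1, with the range of 55.5% to 91.6% at 20 per group for 0.8 to 1.2 SD. State that the transfer of the section 14 effect to the log scale is an assumption.

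Another single prespecified CFU variable, or another valid multiplicity method such as a fixed testing sequence, would also close the gap.

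The cost is a few sentences in sections 14 and 20. No new measurements are needed, because S1 and S2 are already taken in every group. The downside is power per contrast slightly below the stated 80% without S1. Dunnett at d = 1 would need about 21–22 per group to reach it. The shortfall at 20 is small and depends on an uncertain effect size, so restating the figure is preferable to enrolling more.
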